5.5 Investigational Drug Description

CDX-301

CDX-301 is a recombinant human Flt3 ligand (Flt3L) that is a hematopoietic growth factor which is structurally related to stem cell factor (SCF) and macrophage colony-stimulating factor (M-CSF). It is naturally expressed as a membrane bound or secreted protein and binds to fms-like tyrosine kinase 3 (Flt3; or FLK-2, STK-1; CD135), a receptor tyrosine kinase in the same family as c-kit, c-fms, and PDGFR A and B.

Each 2 mL clear borosilicate glass vial contains 2.5 mg/mL CDX-301 glycoprotein in a 1.0 mL (with an overfill to 1.2 mL) volume of buffered solution composed of 10 mM sodium phosphate, 140 mM NaCl, pH 7.0. CDX-301 Drug Product is formulated as a sterile solution intended for single-use subcutaneous administration.

Investigational Drug Supply

An initial study drug shipment will be provided following receipt of all required documents. Additional supplies should be ordered with at least one week advance notice using a form supplied by Celldex.

Storage

All study supplies must be stored in a secured area with limited, approved

access. CDX-301 temperature must be maintained between 2° to 8°C (36 to 46°F) and monitored daily. Deviations in storage conditions must be reported to [contact] within 24 hours of awareness.

CDX-301 Dose Calculation

The individual dose is calculated using the actual baseline body weight of the subject according to the calculations below. All subjects will receive 75 µg/kg of CDX-301 at each administration.

$$\text{Body Weight (kg)} \times \text{Dose Level (75}\mu\text{g/kg)} = \text{Desired Dose (}\mu\text{g)}$$

$$\text{Desired Dose (}\mu\text{g)} \div 2500 \mu\text{g/mL} = \text{Volume of CDX-301 (mL)}$$

For example, for an 80 kg subject, the total dose required to deliver the 75 µg/kg dose would be 6000 µg. The calculated volume required from the 2500 µg/ml CDX-301 stock solution to obtain 6000 µg of CDX-301 would be 2.4 ml. See example formula below:

$$(80 \text{ kg} \times 75 \mu\text{g/kg}) \div 2500 \mu\text{g/mL} = 2.4 \text{ mL (Three vials will be needed to administer this dose)}$$

CDX-301 Preparation

CDX-301 liquid should be withdrawn from the vial gently, avoiding foaming and excess shearing. As the maximum volume of any individual injection will be 2.0 ml, the dose may be split into up to 3 separate syringes/subcutaneous injections as needed to administer the required volume.

CDX-301 Administration

CDX-301 will be administered as a daily subcutaneous injection. The injection site may be rotated between the extremities. CDX-301 injections should not be given to areas of skin with conditions such as scarring, tattoos or persistent injection site reactions that will not allow easy access for study drug administration or evaluation of localized adverse events. CDX-301 administration will be performed within the clinical setting by trained staff personnel.

6.0 STATISTICAL CONSIDERATIONS

6.1 Primary Endpoint – Progression-Free Survival

Cohort 1:

We will present the progression free survival rate at 4 months as a percentage along with its 95% confidence interval. In addition, Progression-free survival will be examined using the Kaplan-Meier method.

A total of 29 patients will be enrolled in Cohort 1 to test the null hypothesis (H0) that PFS4 is 20% or less versus the alternative hypothesis (H1) that PFS4 is 40.5% or greater. If at least 10 of 29 patients are alive without progression at 4 months, this study regimen will be considered for further development in this setting. Using this criterion, the probability of pursuing this regimen for further study if the true PFS4 is $\geq 40.5\%$ is at least 80%. The chance that this regimen will be considered for further development if the true PFS4 is 20% or lower is at most 5%.

Cohort 2:

A total of 20 patients will be enrolled in Cohort 2. We will estimate the PFS4 probability along with its 95% confidence interval using the Kaplan Meier survival procedure. We will also present median progression-free survival duration.

We assume a type-II censoring mechanism in this study, where the study will continue until 16 events occur in this cohort. We also hypothesize that progression-free survival durations will follow an exponential distribution with a mean of 5.8 months. Under these assumptions, a sample size of 20 subjects would produce a two-sided 95% confidence interval width of 4.4 months for the median progression-free survival duration (95% CI: 2.6 months to 7.0 months).

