4.3 Primary Endpoint

- The primary endpoint is progression-free survival rate at four months (PFS4), defined as the rate estimate of the percentage of patients who are alive and progression-free at 16 weeks (~4 months) after initiation of study therapy.

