4.4 Secondary Endpoints

- Dose limiting toxicities (DLTs): For the purposes of this study, a DLT will be defined as any treatment-emergent grade 3-5 toxicity, scored using the Common Terminology Criteria for Adverse Events (CTCAE) version 4.0, and occurring within 30 days after treatment with SBRT in combination with FLT3 ligand therapy. Asymptomatic laboratory abnormalities (e.g.: leukocytosis) that do not require intervention will not be counted as DLTs. For subjects who receive more than one “cycle” of SBRT and FLT3 ligand, only adverse events that occur after the first cycle will be scored as potential DLTs.
- Clinical/radiographic endpoints: These will include radiographic response rates, disease progression, and death. Radiographic endpoints will be scored using according to immune-related response criteria (irRC).[31] To allow comparison of our data with historical experiences, we will also score radiographic findings using RECIST 1.1 criteria.[32] Pre- and post-treatment assessments will include PET/CT imaging, so that we can assess responses using PERCIST criteria[33] and with volumetric PET measures, which have been shown to be prognostic in metastatic NSCLC patients [34, 35] and predictive of clinical outcomes in advanced NSCLC patients treated with targeted therapy.[36] SBRT target lesions will not be considered in the radiographic evaluation of treatment responses, as rates of treatment response and disease control in lesions treated

with SBRT have been shown to be excellent and may not be indicative of the effectiveness of combined modality therapy.

- Potential surrogate outcomes for clinical endpoints: We will collect plasma samples at regular intervals to facilitate monitoring immune responses such as DC expansion. We will also follow T-cell inducible costimulator (ICOS) expression. ICOS is a member of the immunoglobulin superfamily. Responses to immunotherapy have been associated with increased ICOS expression on CD8+ T-cells, particularly following CTLA-4 blockade.[37-40] We will follow serum levels of high-mobility group box 1 (HMGB1), whose release has been linked to antitumor immune responses.[41, 42] Flow cytometry will be performed to track measures of DC maturation such as CD83 and CD86 expression.[43] Other correlative studies will be performed in collaboration with [name] laboratory and the study sponsor.

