6.3 Other Secondary Endpoints

irRC, RECIST, and PERCIST response rates, based on first post-treatment imaging, will be reported using descriptive statistics. Rates of disease-free and overall survival will be reported using actuarial methods. Exploratory analyses will be

performed to evaluate surrogate endpoints, including radiographic responses and immune correlates, as predictors of clinical outcomes. We will also perform statistical tests to explore if response rates, time-to-event outcomes, and immune responses correlate with SBRT fraction size.

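### Does Cohort 1's 10-of-29 rule lose its stated 5% error because Sections 4.3 and 6.1 do not name the progression criterion?

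*Combined protocol and SAP*

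**What the plan says.** Section 4.3 sets the primary endpoint as the percentage of patients "alive and progression-free at 16 weeks (~4 months) after initiation of study therapy". It names no progression criterion.

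Section 6.1 uses 29 Cohort 1 patients to "test the null hypothesis (H0) that PFS4 is 20% or less versus the alternative hypothesis (H1) that PFS4 is 40.5% or greater". The rule is a count: "If at least 10 of 29 patients are alive without progression at 4 months, this study regimen will be considered for further development". The error limit is also given there: "The chance that this regimen will be considered for further development if the true PFS4 is 20% or lower is at most 5" per cent. Power at 40.5% is put at 80% or more. No criterion is named here either, and the section does not say where the 20% comes from.

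Criteria appear in Section 4.4, under secondary endpoints. On the clinical and radiographic endpoints it says: "These will include radiographic response rates, disease progression, and death". The next sentence sets the scale: "Radiographic endpoints will be scored using according to immune-related response criteria (irRC". It then adds: "To allow comparison of our data with historical experiences, we will also score radiographic findings using RECIST 1.1 criteria".

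Section 6.3 returns to the scales, but only for response: "irRC, RECIST, and PERCIST response rates, based on first post-treatment imaging, will be reported using descriptive statistics".

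**The concern.** The Cohort 1 decision rests on one integer. Two scorings of the same scans can place a patient on different sides of progression, and neither section that defines the primary test says which scoring enters the count.

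Section 4.4 can be read two ways. Its order favours irRC. Its stated reason for RECIST 1.1, comparability with history, favours RECIST for a test against a fixed rate, if that rate is historical. Two careful analysts could each cite the protocol for a different choice.

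Three things would be at stake:

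- If the count used a more lenient scale than the null, the false-positive rate would exceed 5%.
- If it used a stricter one, power would fall below 80%.
- If the choice were left until the data were read, there would be two chances to reach 10.

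**Working it through.** **Inputs.** From Section 6.1: n = 29, success at 10 or more, null rate 0.20, alternative 0.405, error at most 5%, power at least 80%. The documents give no rate of disagreement between irRC and RECIST 1.1, so every disagreement figure below is an assumption.

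**Step 1: reproduce the plan.** With X the number alive and progression-free, X ~ Bin(29, p) and P(X ≥ c) = Σ C(29,k) p^k (1−p)^(29−k), summed over k = c to 29.

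| Bar c | P(X ≥ c) at p = 0.20 | P(X ≥ c) at p = 0.405 |
|---|---|---|
| 9 | 0.1084 | 0.8917 |
| 10 | 0.0493 | 0.8009 |
| 11 | 0.0197 | 0.6773 |

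Of these bars, only 10 meets both stated limits, so the plan's figures are right. The slack is small: P(X ≥ 10) reaches 0.050 at p of about 0.2005.

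**Step 2: counting scale more lenient than the null's scale.** Suppose a share r of those who have progressed on the null's scale count as progression-free. Then p = 0.20 + 0.80r, and the expected number reclassified is 29 × 0.80 × r = 23.2r.

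| r | Patients | p | P(X ≥ 10) |
|---|---|---|---|
| 2.5% | 0.6 | 0.22 | 0.085 |
| 5% | 1.2 | 0.24 | 0.136 |
| 10% | 2.3 | 0.28 | 0.277 |

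As a fixed shift, if 10 on the counted scale is 9 or 8 on the null's scale, the error is P(X ≥ 9) = 0.108 or P(X ≥ 8) = 0.210 at p = 0.20.

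**Step 3: counting scale stricter.** Suppose a share q of progression-free patients count as progressed. Power is then taken at p = 0.405(1−q) and error at p = 0.20(1−q).

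| q | Power | Error |
|---|---|---|
| 5% | 0.733 (p = 0.3847) | 0.036 (p = 0.19) |
| 10% | 0.654 (p = 0.3645) | 0.026 (p = 0.18) |

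In this direction the limit of at most 5% still holds, and only power is lost.

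**Step 4: either count allowed to win.** Let both scales truly give 20%, with a proportion b of patients progression-free on the first scale only and the same proportion on the second only. The four cells have probabilities 0.20−b, b, b and 0.80−b. The exact multinomial chance that the larger count reaches 10 is 0.060, 0.067, 0.072 and 0.075 for b = 1%, 2%, 3% and 4%.

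**Step 5: does the text leave the scale open?** The bullet in 4.4 covers disease progression and death, which are the two components of PFS. It assigns irRC as the scoring scale without qualification and introduces RECIST 1.1 as an additional scoring with a comparative purpose. Read together, irRC defines progression and RECIST 1.1 is supplementary. No section offers a choice between the two counts for the 10-of-29 rule.

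**The case for a change.** The best case for a change is that 4.4 governs secondary endpoints, and that its one sentence about historical comparison describes what a fixed null rate may need. On that view irRC is only implied, for an endpoint that 4.4 does not formally govern. With so little slack in the rule, one or two patients classified differently could decide the outcome. A short definition would cost no patients, scans or recalculation. Section 2.5 shows that a PFS curve for the first 9 patients already exists, so settling the scale late could look like hindsight.

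Part of this stands. The criterion is implied and not stated, 4.3 does not refer to 4.4, and a reader cannot tell on what scale the 20% was set.

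The rest does not carry. An increase in error needs a mismatch with the null in one particular direction, and the documents show neither the mismatch nor the direction. The two-chances case needs permission to use whichever count succeeds, which the plan does not give; even then the error is 6.0% to 7.5% over the assumed range. The remedy would write down the reading 4.4 already implies and place beside it a RECIST 1.1 result from scoring that 4.4 already requires. The null, sample size and bar would all stay as they are.

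**Conclusion.** No change to the plan follows. The definition is incomplete where the primary endpoint is stated, but 4.4 supplies a sensible default (irRC) and requires the alternative scoring (RECIST 1.1), so a competent analyst can count on irRC and show the RECIST 1.1 count next to it.

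The stated operating characteristics are correct: exact error 4.93% and exact power 80.1%. They are assured only when the count and the 20% null share a scale, but a stricter counting scale would still respect the 5% limit. The larger figures (8.5% to 27.7% by reclassification, 10.8% or 21.0% by a fixed shift) are conditional on assumed one-way disagreement and measure no known defect.

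The consequence is also modest. Section 1.1 describes the aim as exploring efficacy, and reaching the bar only makes the regimen a candidate for further development. The conclusion assumes that 4.4's order is followed and that one count is used throughout. It would need revisiting if the 20% were shown to come from a scale that calls progression earlier than irRC.

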6.2 Secondary Endpoints - Safety and Tolerability

An early stopping rule for safety will be implemented for Cohort 1 as follows. After the first 6 patients have been enrolled, accrual will be temporarily suspended while these patients are monitored for occurrence of DLTs. The trial will be terminated early if more than 1 patient experiences a DLT. If 1 or fewer grade 3 toxicities and 0 grade 5 toxicities are observed after the sixth patient has been observed for 30 days following completion of treatment, the trial will continue until a total of 29 patients have been evaluated. At the end of the trial, the treatment will be considered safe and worthy of further study if no more than 4 patients experience a DLT. For the first six patients enrolled, we will not initiate treatment for more than one patient on the same day.

The target Grade 3 toxicity rate is no more than 10% and a toxicity rate greater than 30% is considered clinically unacceptable. The design specified above has the following operating characteristics: The probability of accepting the treatment for further study if the toxicity rate is unacceptably high ($>30\%$) is at most 4%. In contrast, there is at least an 84% probability of accepting the treatment for further study if the toxicity rate is less than 10%.

The proportion of patients who develop a DLT will be computed. 95% confidence intervals for the DLT rate will be calculated using Clopper-Pearson exact confidence method.

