1.2 Secondary Objectives

- To establish the feasibility and safety of combining SBRT with FLT3 ligand immunotherapy for advanced NSCLC and for other advanced solid tumors after treatment with immune checkpoint inhibitors targeting the PD-1/PD-L1 axis.
- To quantify and evaluate potential surrogate outcomes for clinical efficacy of this treatment approach, including radiographic responses, immunologic responses, and circulating tumor cell levels.

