4.0 STUDY DESIGN

4.1 General Design

This is a single-arm, phase II study with two cohorts. A total of 29 patients will be enrolled in Cohort 1, and 20 patients will be enrolled in Cohort 2. All patients will be treated with SBRT to a single pulmonary or extrapulmonary lesion as well as FLT3 ligand immunotherapy. Patients will be followed closely for the development of any

treatment-related toxicities. Whole-body PET/CT imaging will be performed prior to study entry and every 8 weeks thereafter.

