9.0 DATA SAFETY AND MONITORING BOARDS

All trials initiated by the Montefiore Medical Center are subject to oversight by the Data Safety Monitoring Board (DSMB). This board meets two times per year with any additional meetings scheduled when needed. The responsibilities are as follows:

- Familiarize themselves with the research protocol (s)
- Review interim analyses of outcome data and cumulative toxicity data summaries to determine whether the trial should continue as originally designed, should be changed, or should be terminated based on these data.
- The DSMB reviews trial performance information such as accrual information.
- The DSMB also determines whether and to whom outcome results should be released prior to the reporting of study results.
- All adverse events are reviewed by the committee with assurances that these have been in fact sent for review to all pertinent IRBs.
- Review of reports of related studies to determine whether the monitored study needs to be changed or terminated.
- Review major proposed modifications to the study prior to their implementation (e.g., termination, dropping an arm based on toxicity results or other reported trial outcomes, increasing target sample size).

- Following each DSMB meeting, provide the study leadership with written information concerning findings for the trial as a whole related to cumulative toxicities observed and any relevant recommendations related to continuing, changing, or terminating the trial. The study leadership will provide information on cumulative toxicities and relevant recommendations to the local PI to be shared with their IRB's.

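### After Cohort 1's six-patient look, section 6.2 sets no cohort-level DLT boundary that pauses accrual, and it sets none for Cohort 2; beyond that point monitoring rests on discretionary DSMB review

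*Combined protocol and SAP*

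**What the plan says.** Section 4.1 fixes the sizes: "A total of 29 patients will be enrolled in Cohort 1, and 20 patients will be enrolled in Cohort 2". Section 1.2 makes safety an objective for both populations: "To establish the feasibility and safety of combining SBRT with FLT3 ligand immunotherapy for advanced NSCLC and for other advanced solid tumors".

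The numerical safety rule is in section 6.2 and is introduced for one cohort only: "An early stopping rule for safety will be implemented for Cohort 1 as follows". It has three parts.

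- A look: "After the first 6 patients have been enrolled, accrual will be temporarily suspended while these patients are monitored for occurrence of DLTs", with the boundary "The trial will be terminated early if more than 1 patient experiences a DLT".
- Continuation if the look is passed: "the trial will continue until a total of 29 patients have been evaluated".
- An end-of-trial verdict: "the treatment will be considered safe and worthy of further study if no more than 4 patients experience a DLT".

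Section 6.2 takes 10% as the target toxicity rate and anything above 30% as unacceptable. It states an acceptance probability of at most 4% at the high rate and at least 84% at the low one.

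Other provisions carry no cohort limit. Under section 9.0 the DSMB reviews cumulative toxicity and can change or end the trial; on timing, "This board meets two times per year with any additional meetings scheduled when needed". Section 10.2 sends SAEs to the IRB and DSMB within 24 hours. Sections 5.2 and 5.3 set rules for the individual patient with toxicity.

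**The concern.** The verdict allows at most four patients with a DLT, so the fifth settles it. From then on, further Cohort 1 enrolment cannot change the safety conclusion, yet 6.2 directs accrual on to 29 and names no count at which anyone must stop and look. Patients could be given a combination that section 7.2 describes as a first, with its full range of toxicities unknown, after the trial's own safety criterion has failed.

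Cohort 2 was added later (end of section 2), and 6.2 was not extended to it. Its safety objective has neither a look nor a DLT limit. The DSMB is given no DLT count that would prompt one of its additional meetings.

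**Working it through.** **Inputs.** From 4.1: 29 and 20 patients. From 6.2: look at 6, stop at 2 or more DLTs, accept at 4 or fewer of 29, reference rates 10% and 30%. From 4.4: a 30-day DLT window. A rate of 20% is added as an intermediate case. DLTs are taken as independent with common probability p. Write b(x; n, p) for the binomial probability and B(k; n, p) for its cumulative sum.

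**1. The plan's own figures.** Using only the final rule, B(4; 29, p) = 0.038 at 30% and 0.842 at 10%. These match the stated 4% and 84%, so the limit of four belongs to Cohort 1's 29 patients. With the look included,

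P(accept) = b(0; 6, p) × B(4; 23, p) + b(1; 6, p) × B(3; 23, p).

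- 30%: 0.1176 × 0.1356 + 0.3025 × 0.0538 = 0.032.
- 10%: 0.5314 × 0.9269 + 0.3543 × 0.8073 = 0.779.

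The stated 84% thus leaves out the look. That is a separate matter; 0.779 and 0.032 are the baseline used here.

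**2. How often a fifth DLT follows a passed look.** A trial that passes the look is either accepted or reaches a fifth DLT, so P(fifth) = P(pass) − P(accept).

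- 30%: 0.4202 − 0.0322 = 0.388 (92.3% of trials that pass).
- 20%: 0.6554 − 0.2479 = 0.407 (62.2% of trials that pass).
- 10%: 0.8857 − 0.7786 = 0.107 (12.1% of trials that pass).

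**3. How many patients are still to enrol.** With m = i − 6, the fifth DLT falls on patient i with probability

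h(i) = b(0; 6, p) × C(m−1, 4) p⁵(1−p)^(m−5) + b(1; 6, p) × C(m−1, 3) p⁴(1−p)^(m−4).

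The mean number still to enrol, given a fifth DLT, is Σ(29 − i)h(i) / Σh(i). Multiplying by P(fifth) averages it over all trials.

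| True rate | P(fifth DLT) | Median position | Mean still to enrol, given a fifth DLT | Mean over all trials |
|---|---|---|---|---|
| 30% | 0.388 | patient 19 | 9.86 | 0.3879 × 9.86 = 3.8 |
| 20% | 0.407 | patient 22 | 7.04 | 0.4075 × 7.04 = 2.9 |
| 10% | 0.107 | patient 25 | 4.89 | 0.1071 × 4.89 = 0.5 |

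**4. Reporting lag.** Step 3 treats each DLT as known before the next enrolment. The documents give no accrual rate, so the lag is an assumption. If L patients enrol before the fifth DLT is known, 29 − i becomes max(0, 29 − i − L).

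| L | Mean at 30% | Mean at 20% |
|---|---|---|
| 0 | 9.9 | 7.0 |
| 2 | 7.9 | 5.2 |
| 4 | 6.1 | 3.7 |
| 6 | 4.4 | 2.4 |

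**5. Effect of a pause at the fifth DLT.** Acceptance needs four or fewer, so every paused trial is already one that fails. P(accept) stays at 0.779 (10%) and 0.032 (30%). At a 10% rate the pause would occur in at most 10.7% of trials.

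**6. Cohort 2.** At 30%, 20 × 0.30 = 6 DLTs are expected, with no boundary. If Cohort 1's count were reused, P(5 or more of 20) would be 0.043 at 10%, 0.370 at 20% and 0.762 at 30%. It would miss a 30% rate with probability 1 − 0.762 = 0.238.

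**The case against.** The strongest reply is that section 6.2 is not the whole safety plan. The DSMB may stop or change the trial on cumulative toxicity, can meet outside its two scheduled meetings, and receives SAE reports within 24 hours. The patient-level DLT and leukocytosis rules apply to everyone. All of this stands. A reader might infer that Cohort 2 has no safety rule, or that all 20 patients would be treated whatever the DLT rate. The documents do not support that: what is missing is a numerical trigger, not oversight. Discretion softens the gap without closing it, because nothing says when an additional meeting is needed, and patient-level rules protect the patient with the DLT rather than the next one enrolled.

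A reader might also take the limit of four as a count over all 49 patients, since the sentence refers to the end of the trial. The paragraph opens with Cohort 1 and has just named 29 patients, and the stated 4% and 84% match four or fewer of 29. That reading is excluded.

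Nor can the boundary of more than one DLT be read as running throughout. Acceptance at a 10% rate would then be 0.199 against the stated 84%, and the limit of four would have no purpose.

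Two further points temper the contrast between cohorts. Cohort 1 also allows extrapulmonary targets and prior PD-1 therapy. Cohort 2 was added after results in nine subjects, more than the six in the look. Part of that early-experience section was not available to this review, so no conclusion here assumes anything about its safety content.

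**Conclusion.** The point holds in a limited form. There is no pre-specified cohort-level DLT boundary after patient 6 in Cohort 1, and none in Cohort 2. As written, Cohort 1 proceeds to 29 after its safety verdict is fixed, unless the DSMB intervenes at its discretion.

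The size is moderate. The 9.9 patients at a 30% rate (7.0 at 20%) is the mean only in trials that pass the look and then reach a fifth DLT; over all trials it is 3.8 (2.9 at 20%). With a lag of two to six patients, the conditional mean is 7.9 to 4.4 at 30% and 5.2 to 2.4 at 20%. These figures rest on independent DLTs with a constant rate, and on lags that the documents do not give.

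This is a cheap improvement in patient protection, not an error that invalidates the Cohort 1 design. The Cohort 1 trigger follows from the plan's own limit. The right count for Cohort 2 is open to judgement.

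**What to change.** In sections 6.2 and 9.0, state that accrual to Cohort 1 is suspended and an ad hoc DSMB review is called when a fifth Cohort 1 patient has a DLT. This should be a suspension for review, not automatic termination.

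For Cohort 2, state a DLT count that triggers DSMB review, chosen for 20 patients, and give its operating characteristics at the plan's 10% and 30% rates. Reusing five or more is one option, but its 24% miss rate at 30% should be weighed against the 4% standard that 6.2 sets for Cohort 1.

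The cost is protocol wording, with no extra patients or data. If the true rate is 10%, up to 10.7% of trials would see a Cohort 1 pause, all of them trials that would be declared not safe anyway. Four-month progression-free survival data would be lost only if the DSMB then stopped the cohort.

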Figure 7 – Kaplan-Meier curves for overall survival and progression-free survival for the first 9 study subjects

Based on these exciting results, which were presented at the Clinical Trials Plenary Session at the 2018 AACR Annual Meeting, we are adding a second study cohort to this protocol. This group will include patients with advanced solid tumors other than NSCLC who have previously been treated with immune checkpoint therapy targeting the PD-1/PD-L1 axis.

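### The acceptance probability of at least 84% in section 6.2 leaves out the six-patient stop; with the stop triggered by DLTs it is 77.9% at a 10% DLT rate

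*Combined protocol and SAP*

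**What the plan says.** Section 6.2 of the combined protocol and SAP describes the Cohort 1 safety rule in two steps.

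- **Look after six patients.** Enrolment pauses once six patients are in, so that they can be watched for DLTs. The stopping criterion at this look is: "The trial will be terminated early if more than 1 patient experiences a DLT". A further sentence gives the condition for going on to 29 patients: "If 1 or fewer grade 3 toxicities and 0 grade 5 toxicities are observed" once the sixth patient has 30 days of follow-up after treatment.
- **End of trial.** The treatment is accepted as safe if no more than 4 of the 29 patients have a DLT.

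The section then gives the benchmark rates. "The target Grade 3 toxicity rate is no more than 10" percent, and a rate above 30% is unacceptable. It continues: "The design specified above has the following operating characteristics". The first is a chance of acceptance of at most 4% when the rate exceeds 30%. The second is: "In contrast, there is at least an 84% probability of accepting the treatment for further study if the toxicity rate is less than 10" percent.

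Section 4.4 defines the event counted: "a DLT will be defined as any treatment-emergent grade 3-5 toxicity", within 30 days and after the first cycle only, leaving out asymptomatic laboratory abnormalities that need no intervention.

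**The concern.** The two probabilities are attributed to the whole design, and the design includes the six-patient stop. A stop can only remove trials that would otherwise have ended in acceptance. If the 84% was calculated from the final boundary alone, it overstates the chance that an acceptably safe treatment passes.

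These are the only two operating characteristics given for the safety rule. Anyone judging whether the rule is too strict, or reading a rejection at the end of the trial, would rely on them.

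The calculation also depends on what triggers the stop and on which event the rate refers to. Section 6.2 words the trigger in two ways that do not agree, and it names the event in two ways.

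**Working it through.** **Inputs, all from section 6.2.** First stage 6 patients, continue with 0 or 1 DLT; total 29, so 23 more; accept with 4 or fewer DLTs in all; rates 10% and 30%. I read the toxicity rate p as the per-patient DLT rate and treat patients as independent.

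**Step 1: reproduce the stated figures.** Ignoring the stop, acceptance is P(X ≤ 4) with X ~ Bin(29, p).

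- p = 0.10: 0.8416
- p = 0.30: 0.0379

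These match the stated 84% and 4%, so both figures appear to be one-stage values.

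**Step 2: include the stop as more than 1 DLT in 6.**

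Acceptance = P(Bin(6,p) = 0) × P(Bin(23,p) ≤ 4) + P(Bin(6,p) = 1) × P(Bin(23,p) ≤ 3)

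- p = 0.10: 0.5314 × 0.9269 + 0.3543 × 0.8073 = 0.7786
- p = 0.30: 0.1176 × 0.1356 + 0.3025 × 0.0538 = 0.0322

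A simulation of 2,000,000 trials gave 0.7788 and 0.0323.

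| True DLT rate | One stage | Two stage | Early termination |
|---|---|---|---|
| 5% | 98.6% | 95.8% | 3.3% |
| 8% | 92.2% | 86.9% | 7.7% |
| 9% | 88.6% | 82.7% | 9.5% |
| 10% | 84.2% | 77.9% | 11.4% |
| 30% | 3.8% | 3.2% | 58.0% |

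Two-stage acceptance equals 84% at p = 0.087. The claim covers every rate below 10%, so it fails between about 8.7% and 10%. False rejection at 10% is 100 − 77.9 = 22.1%, against an implied 100 − 84 = 16%.

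**Step 3: set the two stage 1 sentences side by side.** A DLT is grade 3 to 5.

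- One grade 5 DLT and no other among the six: not more than 1 DLT, so the termination sentence does not apply; but a grade 5 event has occurred, so the continuation sentence is not met either. No consequence is stated.
- Two grade 4 DLTs and no other: more than 1 DLT, so terminate; but no grade 3 and no grade 5 event, so continue. Both sentences apply.

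**Step 4: see whether the other wording restores 84%.** Suppose the continuation sentence alone governs stage 1, with one worst grade per patient and the final limit still 4 DLTs in 29. The result then depends on the mix of grades among DLTs. The documents do not give one, so these shares are assumptions.

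| Grade 4 share | Grade 5 share | Acceptance at 10% DLT rate |
|---|---|---|
| 10% | 0 | 79.0% |
| 20% | 0 | 80.0% |
| 50% | 0 | 82.5% |
| 0 | 5% | 76.4% |
| 0 | 10% | 75.0% |
| 0 | 20% | 72.1% |
| 20% | 10% | 76.9% |

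With no grade 5 events, 84% is reached only when about 85% of DLTs are grade 4. At a 30% DLT rate the same mixes give 2.9% to 3.6%.

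If both sentences must be satisfied to continue, acceptance at 10% is 77.9% with no grade 5 events and lower with some (75.0% at a 10% grade 5 share).

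**The case against.** The strongest objection concerns the event. The 10% target is worded as a Grade 3 toxicity rate, and section 4.4 leaves some grade 3 events out of the DLT count: asymptomatic laboratory abnormalities, events after 30 days, and events after later cycles. If the rate in the claim is this broader one, a 10% toxicity rate means a DLT rate below 10%. With an assumed 13% of such toxicities not counting as DLTs, the DLT rate is 0.10 × 0.87 = 8.7% and two-stage acceptance is about 84.0%. With 20% it is 86.9%, and with 30% it is 90.5%. This is arithmetically right, and it limits the finding to the DLT reading. It does not rescue the stated figure: the documents give no such share, and 84% is exactly what the one-stage formula gives when 10% is taken as the DLT rate. Counting grade 3 only as the rate, with grades 4 and 5 added to the DLTs, would push acceptance the other way.

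A second objection is that 77.9% becomes an upper limit if the continuation sentence is an added condition. That is true of that reading, which also misses 84%. It is not true when the continuation sentence stands alone, so 77.9% is best given as the value for one stated rule.

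A third is that little depends on this. That largely stands. The omission makes the rule look less strict than it is, the 4% figure is safe, and the failing range is narrow. Section 2.5 also shows "progression-free survival for the first 9 study subjects", which suggests that the six-patient look has passed, although the text available does not report its outcome. Conditional on passing it under the DLT rule, acceptance is 0.7786 / 0.8857 = 87.9% at 10% and 7.7% at 30%; section 6.2 does not state these values.

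**Conclusion.** The concern holds and is minor. Read as a DLT rate, the 84% belongs to a design without the six-patient stop. With the stop at more than 1 DLT, acceptance at a 10% rate is 77.9%, about 6 points lower, and the claim is false for rates between about 8.7% and 10%. The statement of at most 4% acceptance at 30% stays true under every reading tested.

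The result rests on exact binomial arithmetic, independence between patients, and the rate being the per-patient DLT rate. On that basis no stage 1 rule can take acceptance at 10% above 84.2%, since stopping only removes acceptances. The conflict between the two stage 1 sentences is a separate defect of wording, and it decides which figure finally applies.

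**What to change.** 1. Reconcile the termination and continuation sentences in section 6.2 so that every outcome in the first six patients has one stated consequence. Which rule applies is for the sponsor and investigators to state.
2. Use one event name for the target rate, the stop and the final boundary, consistent with section 4.4.
3. Restate the operating characteristics for the reconciled two-stage rule. If DLTs alone trigger the stop, the text could read: *The probability of accepting the treatment is about 78% at a true DLT rate of 10%, 87% at 8%, 96% at 5% and 3% at 30%. The probability of early termination is about 11% at 10% and 58% at 30%.* Under a rule that depends on grade, recompute the figures and state the grade mix assumed.

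The cost is two or three sentences, and one stated figure becomes less favourable. The sample size, the final boundary of 4 in 29 and the primary test in section 6.1 are unaffected.
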